## 16.6. PREGNANCIES

Pregnancies will be presented for the Safety analysis set.

The following listing is planned for presentation:

- Reported pregnancies.

The following pregnancy variables, as presented in the planned TLF shells, will be collected on the Pregnancy Notification eCRF:

- Pregnancy test:
  - o Date of test.
  - o Type:
    - Serum.
    - Urine.
  - o Result:
    - Positive.
    - Negative.
- Current pregnancy information:
  - o Estimated conception date.
  - o Estimated delivery date.
- Current pregnancy outcome:
  - o Date of delivery/outcome.
  - o Outcome:
    - Normal.
    - Abnormal.
- Health status of mother.
- Health status of child.
- Additional information.

### 16.6.1. DERIVATIONS

Based on the aforementioned the following variable, as presented in the planned TLF shells, will be derived:

- Study day of the most recent vaccination:
  - o Calculated relative to Day 0 vaccination (refer to Section 6.1: Reference Start Date and Study Day).
- Relative day:
  - o Calculated relative to most recent vaccination (refer to Section 6.1: Reference Start Date and Study Day).

---

Document: Aeras\_C-040-404\_SAP\_V2\_0

Author: [name]

Version Number:

2.0

Version Date:

29SEP2017

Template No: CS\_TP\_BS016 – Revision 3

Reference: CS\_WI\_BS005

Effective Date: 01May2012

Copyright © 2012 Quintiles Transnational Corp. All rights reserved.

The contents of this document are confidential and proprietary to Quintiles Transnational Corp. Unauthorized use, disclosure or reproduction is strictly prohibited.

## 17. DATA NOT SUMMARIZED OR PRESENTED

The following eCRF data will not be presented:

- Immediately Reportable Event eCRF:
  - o Immediately reportable events would be reported as part of the relevant domain's analysis.

---

Document: Aeras\_C-040-404\_SAP\_V2\_0

Author: [name]

Version Number:

2.0

Version Date:

29SEP2017

Template No: CS\_TP\_BS016 – Revision 3

Reference: CS\_WI\_BS005

Effective Date: 01May2012

Copyright © 2012 Quintiles Transnational Corp. All rights reserved.

The contents of this document are confidential and proprietary to Quintiles Transnational Corp. Unauthorized use, disclosure or reproduction is strictly prohibited.

## APPENDIX 1. PROGRAMMING CONVENTIONS FOR OUTPUTS

Refer to the latest version of the relevant TLF shells.

### STUDY VISITS

All study visits will be indicated as Visit in the relevant outputs (TLFs). The visits will be presented in the following order:

- Screening.
- Day x, where x = 0, 3, 7, 28, 56, 63, 70, 84.
- Month x, where x = 6, 9, 12, 15, 18, 21, 24, 27, 30.
- Any Time Point (if relevant).

### FOOTNOTES

Footnotes will be ordered as follows:

- Non-standard abbreviations, separated by a full stop.
- n = Number of participants... N = Total number of participants... % = Percentage of participants.
- Definitions.
- Footnotes pertaining to statistical methodology.
- If coding is presented, the version of the coding dictionary used.
- Study-specific footnotes to clarify data points within the specific presentation.

### OUTPUT HEADERS

Refer to the relevant set of TLF shells for the specific output header format.

### OUTPUT FOOTERS

Refer to the relevant set of TLF shells for the specific output footer format.

### DECIMAL PRECISION

All values will be rounded using the SAS® function ROUND, as the last step prior to presentation. All computed percentages (%) will be presented using one decimal place. If the original data has N decimal places (as derived

---

Document: Aeras\_C-040-404\_SAP\_V2\_0  
Author: [name]

Version Number: 2.0  
Version Date: 29SEP2017

Template No: CS\_TP\_BS016 – Revision 3  
Effective Date: 01May2012

Reference: CS\_WI\_BS005

from the raw data), then the summary statistics for quantitative data are to contain the following number of decimal places (with a maximum of 3 places):

- Minimum and maximum: N.
- Mean and median: (N+1).
- Standard deviation: (N+2).

All p-values will be presented with 4 decimal places, if less than 0.0001 (after rounding to 4 decimal places) the p-value will be displayed as <0.0001. Odds ratios will be presented to 3 decimals and CIs will be presented to 2 decimals.

## DATES & TIMES

Dates will be displayed as DDMMYYYY. Times will be displayed as HH:MM (24-hour clock).

## SPELLING FORMAT

English US.

## LISTINGS

All listings will be sorted primarily by treatment group, in the order specified as applicable to the specific listing.

## PRESENTATION NOTES

- In all listings, participants will be identified by means of the 16-digit participant identifier.
- Output margins should be top 1.5 inch and 1 inch on left, right and bottom.
- Each TLF will be produced as a separate stand-alone document.
- If separate presentations are required for analysis set or subgroups then these should be presented as stand-alone.
- All spelling is to adhere to English (US).
- All TLFs will be presented in a landscape format, as far as is feasible.
- The content of all tables and listings will be uppercase (excluding titles, column headers and footnotes), that is the 'Reported Term' in the medical conditions listing, for example.
- For all AE/CM/MH listings all coded terms will not be presented in uppercase, but rather as coded (sentence case) for differentiation from verbatim terms.

---

Document: Aeras\_C-040-404\_SAP\_V2\_0  
Author: [name]

Version Number: 2.0  
Version Date: 29SEP2017

Template No: CS\_TP\_BS016 – Revision 3  
Effective Date: 01May2012

Reference: CS\_WI\_BS005

- The margin, page size and line size specifications as stipulated below will be used for the presentation of all TLFs:

	Landscape	Portrait
Paper Size	U.S. Letter (8.5 x 11 inch)	U.S. Letter (8.5 x 11 inch)
Margins (Inches):		
Top	1.25	1
Bottom	1	1
Left	1	1.25
Right	1	1
Header (Inches)	0.5	0.5
Footer (Inches)	0.5	0.5
SAS® Specifications:		
PAGESIZE	46 (8 point size, Courier)	67 (8 point size, Courier)
	41 (9 point size, Courier)	60 (9 point size, Courier)
LINESIZE	134 (8 point size, Courier)	93 (8 point size, Courier)
	119 (9 point size, Courier)	82 (9 point size, Courier)

Document: Aeras\_C-040-404\_SAP\_V2\_0

Author: [name]

Version Number:

2.0

Version Date:

29SEP2017

Template No: CS\_TP\_BS016 – Revision 3

Reference: CS\_WI\_BS005

Effective Date: 01May2012

Copyright © 2012 Quintiles Transnational Corp. All rights reserved.

The contents of this document are confidential and proprietary to Quintiles Transnational Corp. Unauthorized use, disclosure or reproduction is strictly prohibited.

## APPENDIX 2. PARTIAL DATE CONVENTIONS

Imputation will only be performed for partially or completely missing AE start dates. Imputed AE start dates will not be presented in the listings and are only used to assign AEs to the relevant post-vaccination reporting window.

AE Start Date			Criterion	Action
Day	Month	Year		
Missing	Known	Known	AE start month and year are the same as the month and year of only one study vaccination (Day 0 or Day 56)	Assign the missing day as the day of the relevant study vaccination in the coinciding month and year
			AE start month and year are the same as the month and year of more than one study vaccination (Day 0 or Day 56)	Assign the missing day as the day of the earliest study vaccination in the coinciding month and year
			AE start month and year are not the same as the month and year of any of the study vaccinations (Day 0 or Day 56) and known to be in between study vaccinations	Assign the missing day as the first day of the month
			AE start month and year are not the same as the month and year of any of the study vaccinations (Day 0 or Day 56) and known to be prior to all study vaccinations	Assign the missing day as the last day of the month
			AE start month and year are not the same as the month and year of any of the study vaccinations (Day 0 or Day 56) and known to be after all study vaccinations	Assign the missing day as the first day of the month
Missing	Missing	Known	AE start year is the same as the year of only one study vaccination (Day 0 or Day 56)	Assign the missing day and month as the day and month of the relevant study vaccination in the coinciding year
			AE start year is the same as the year of more than one study vaccination (Day 0 or Day 56)	Assign the missing day and month as the day and month of the earliest study vaccination in the coinciding year
			AE start year is not the same as the year of any of the study vaccinations (Day 0 or Day 56) and known to be prior to all study vaccinations	Assign the missing day and month as 31 December

Document: Aeras\_C-040-404\_SAP\_V2\_0

Author: [name]

Version Number:

2.0

Version Date:

29SEP2017

Template No: CS\_TP\_BS016 – Revision 3

Reference: CS\_WI\_BS005

Effective Date: 01May2012

Copyright © 2012 Quintiles Transnational Corp. All rights reserved.

The contents of this document are confidential and proprietary to Quintiles Transnational Corp. Unauthorized use, disclosure or reproduction is strictly prohibited.

AE Start Date			Criterion	Action
Day	Month	Year		
			AE start year is not the same as the year of any of the study vaccinations (Day 0 or Day 56) and known to be after all study vaccinations	Assign the missing day and month as 01 January
Missing	Missing	Missing	-	Assign the missing date as the date of Dose 1 of study vaccination

Document: Aeras\_C-040-404\_SAP\_V2\_0

Author: [name]

Version Number:

2.0

Version Date:

29SEP2017

Template No: CS\_TP\_BS016 – Revision 3

Reference: CS\_WI\_BS005

Effective Date: 01May2012

Copyright © 2012 Quintiles Transnational Corp. All rights reserved.

The contents of this document are confidential and proprietary to Quintiles Transnational Corp. Unauthorized use, disclosure or reproduction is strictly prohibited.

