members of the study team designated in writing by the principal investigator. The onset and resolution dates of the event and action taken in response to the event will be documented. All adverse events must be followed until resolution is demonstrated. The resolution date will be recorded on the CRF as the last date on which the subject experienced the adverse event. If an adverse event resolution date is uncertain the principal investigator or designee should estimate the completion date based on medical judgment and interview of the subject. Approximate dates of resolution from interviews may be taken as adverse event resolution dates. Some examples of estimation of adverse event resolution are: 1) an asymptomatic laboratory abnormality on one visit that has not been followed-up between visits but has resolved by the next visit may be assumed to have resolved by the midpoint of the intervisit interval; 2) A resolved adverse event that was treated may be assumed to have been resolved by the end of treatment. Adverse events that are still present at the end of the trial should be recorded as ongoing. Information recorded on the CRF must be substantiated in the source documents. If an adverse event evolves into a condition that becomes “serious,” it will be designated as serious on the Adverse Event CRF and a Supplemental SAE Report (SAER) form will be completed.

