### 16.1.4. SOLICITED AND INJECTION SITE ADVERSE EVENTS (AEs)

In the database all AEs were reported as either solicited or unsolicited, however the database categorization will not be used to report AEs as either solicited or unsolicited. All AEs will be assigned as either solicited or unsolicited based on the PT (refer to APPENDIX 3: Solicited and Injection Site Adverse Event (AE)) and post-vaccination reporting window (refer to Section 16.1.9: Adverse Event (AE) Post-vaccination Reporting Window for a description of the post-vaccination reporting windows).

Local and systemic solicited AE incidence tables will be presented as follows:

- Solicited AE category (local, systemic).
- PT (descending frequency of total number of participants with events reported within each solicited AE category).

The following incidence tables will be presented by PT only:

- Incidence of solicited AEs.
- Incidence of related solicited AEs.
- Incidence of related solicited AEs by dose at onset (refer to Section 16.1.8: Adverse Event (AE) Dose at Onset (Most Recent Vaccination) for details on the derivation of dose at onset):
  - o Number and percentage (%) of participants with AEs summarized by solicited AE category and PT.

---

Document: Aeras\_C-040-404\_SAP\_V2\_0  
Author: [name]

Version Number: 2.0  
Version Date: 29SEP2017

Template No: CS\_TP\_BS016 – Revision 3  
Effective Date: 01May2012

Reference: CS\_WI\_BS005

- o Includes all solicited AEs within the post-vaccination reporting window (refer to Section 16.1.9: Adverse Event (AE) Post-vaccination Reporting Window for details on the derivation of the post-vaccination reporting window).
- o BCG treatment group will only include Dose 1 at onset AEs.
- Incidence of solicited AEs per cohort and dose at onset (refer to Section 16.1.8: Adverse Event (AE) Dose at Onset (Most Recent Vaccination) for details on the derivation of dose at onset):
  - o Number and percentage (%) of participants with AEs summarized by solicited AE category and PT.
  - o Includes all solicited AEs within the post-vaccination reporting window (refer to Section 16.1.9: Adverse Event (AE) Post-vaccination Reporting Window for details on the derivation of the post-vaccination reporting window).
  - o BCG treatment group will only include Dose 1 at onset AEs.
- Incidence of local solicited AEs by severity and dose at onset:
  - o Number and percentage (%) of participants with AEs summarized by solicited AE category and PT.

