#### **16.1.8. ADVERSE EVENT (AE) DOSE AT ONSET (MOST RECENT VACCINATION)**

A dose at onset will be assigned for all AEs and is defined as the most recent dose prior to the onset of the AE:

- Post any dose (combination of the AEs starting after the Day 0 and Day 56 vaccinations).
- Post-dose 1 (AEs starting after the Day 0 vaccination).
- Post-dose 2 (AEs starting after the Day 56 vaccination):
  - o Only applicable to H4:IC31 and Placebo treatment groups.

The assignment of the dose at onset will be based on the following algorithm:

- Calculate the difference in the AE start date (as collected on the Adverse Events eCRF) and all available study vaccination dates (as collected on the Exposure Day 0 and Exposure Day 56 eCRFs):
  - o Days since dose x: (AE start date – study vaccination dose x date [where x= 1 or 2]).
- From the previous calculation, only consider those doses where the days since dose x is  $\geq 0$  and determine the dose (1 or 2) for which the days since dose x (as calculated in the previous step) is a minimum.
- Assign the dose selected in the previous step as the dose at onset as the specific dose determined in the previous calculation.

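### SAP Appendix 2 imputes partial AE start dates without checking the stop date, so an event known to have ended before dose 2 can be placed in the post-dose-2 reporting window

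*SAP*

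**What the plan says.** SAP Section 7.3 sends all partial or missing AE start dates to Appendix 2. Each criterion there compares the AE start month and year, or the start year alone, with the vaccination dates.

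- **Day missing, month holds one vaccination:** "Assign the missing day as the day of the relevant study vaccination in the coinciding month and year".
- **Day and month missing, year holds one vaccination:** "Assign the missing day and month as the day and month of the relevant study vaccination in the coinciding year".
- **Event known to lie between the doses:** the first of the month is used, but only if "AE start month and year are not the same as the month and year of any of the study vaccinations (Day 0 or Day 56)".

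Appendix 2 adds that imputed dates "are only used to assign AEs to the relevant post-vaccination reporting window".

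The stop date is available. SAP Section 16.1 lists it among the AE eCRF variables, and Protocol Section 5.3 says: "The onset and resolution dates of the event and action taken in response to the event will be documented". The same protocol section asks the investigator to estimate an uncertain resolution date.

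The window matters downstream. SAP Section 16.1.4 sets aside the database's own solicited/unsolicited label: "All AEs will be assigned as either solicited or unsolicited based on the PT" and the post-vaccination reporting window. Section 16.1.2 restricts the AE incidence table to events inside those windows.

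**The concern.** An imputed start date should not contradict data already recorded for the same event. Here it can. The rule fixes the start at the dose-2 day even when the recorded stop date shows that the event was over before dose 2 was given.

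Such an event cannot have followed dose 2. It would still be counted in the window after Day 56, and if its preferred term is on the Appendix 3 list it could be reported as a solicited reaction. Solicited and unsolicited AEs are the primary safety variable (Protocol Section 7.5.1), and safety is a primary objective, so the tables that would carry the error are central ones.

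**Working it through.** The plan gives no figure for this point. The check is to apply the rule as written.

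**Inputs**

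- Imputation rows: SAP Appendix 2.
- Dose-2 window, Day 54 to Day 70: SAP Section 13.1.
- Post-dose-2 windows, 28 days for unsolicited and local solicited AEs and 7 days for systemic solicited AEs: SAP Table 4 (Section 16.1.9).
- Non-serious unsolicited AE collection, 28 days after each dose plus a 5-day visit window, that is 33 days: Protocol Table 3-4.

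**Worked example, day missing (illustrative dates)**

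1. Dose 1 on 25 Jan 2015. Day 56 = 25 Jan + 56 days = 22 Mar 2015.
2. Headache recorded with start Mar 2015 (day missing) and stop 5 Mar 2015. The true onset lies between 1 Mar (Day 35) and 5 Mar (Day 39).
3. March 2015 holds one vaccination, so the imputed start is 22 Mar.
4. Imputed start minus stop = 22 − 5 = 17 days. The event starts 17 days after it ended.
5. 22 Mar is day 0 of the 7-day systemic window after dose 2, and headache is a systemic solicited term in Appendix 3. The event becomes a post-dose-2 systemic solicited AE. Its true onset is outside both the 7-day and the 28-day (or 33-day) window after dose 1.

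**Worked example, day and month missing (illustrative dates)**

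Dose 1 on 15 Nov 2014 puts Day 56 on 10 Jan 2015. An AE with start year 2015 and stop 4 Jan 2015 is imputed to 10 Jan, six days after it ended. The true onset was Day 47 to Day 50.

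**Can another row rescue the case?** No. The between-doses row excludes any month that holds a vaccination.

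**Enumeration.** I took every dose-1 date in 2014 to 2017 (1,461 dates, an illustrative span) with every dose-2 day from 54 to 70 (17 values): 1,461 × 17 = 24,837 combinations.

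| Quantity | Result |
|---|---|
| Combinations with both doses in one calendar month | 0 of 24,837 |
| Pre-dose-2 days in the dose-2 month, pooled | 365,840 |
| Of these, moved to the dose-2 day if the start day is missing | 365,840 (100%) |
| Of these, later than Day 28 | 364,518 / 365,840 = 99.6% |
| Of these, later than Day 33 | 356,668 / 365,840 = 97.5% |

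The one-vaccination row therefore always applies in the dose-2 month when dose 2 is given within its window. Nearly all the true onsets at issue fall outside the dose-1 windows as well.

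**Dose at onset.** Section 16.1.8 says to "only consider those doses where the days since dose x is" zero or more, and takes the nearest such dose. A start on the dose-2 day would give dose 2. But that section names the start date as collected on the eCRF, and Appendix 2 confines imputed dates to window assignment. A partial date cannot be subtracted from a vaccination date, so the plan does not settle what dose such an event receives.

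**The case against.** The strongest reply is that few such events will be on file. Protocol Table 3-4 stops routine non-serious collection at about Day 33 after dose 1, and 97.5% of the days at issue come later. At the Day 56 visit, Protocol Appendix A puts interval history before the injection and AE monitoring after it. SAEs and AESIs are collected throughout, but SAP Table 4 reports them through database lock, so window placement does not decide whether they are included. This stands as a limit on size. It does not remove the problem: Table 3-2 schedules unsolicited AEs at Day 56, and the between-doses row in Appendix 2 shows that the plan expects some events in that interval.

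A second reply is that imputing to the vaccination day is a conservative convention, applied alike to H4:IC31 and Placebo, with AEs summarised descriptively. That also stands. It gives no reason to expect systematic bias between the two blinded arms. Conservatism is a reason to favour the vaccination day when onset is uncertain, not when the stop date excludes it. Database cleaning before lock (SAP Section 4.3) may complete some dates but does not guarantee it.

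Three stronger readings are tempting and are not supported:

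- **About half of day-missing AEs in the dose-2 month are misplaced.** On average 48% of the days in that month precede dose 2, but this is a share of calendar days. It would be a share of AEs only if onsets were recorded evenly through the month, which the collection schedule makes unlikely. It also ignores the condition that the event ended before dose 2.
- **The by-dose tables are wrong.** Only window placement is explicit.
- **The comparison with BCG is materially distorted.** The same event in a BCG participant would be imputed to the first of the month, which is past Day 28 in 97.6% of the combinations, so it would usually be excluded. But the BCG contrast is already unequal by design: one dose against two, and an 84-day against a 28-day local window.

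**Conclusion.** The point holds as a flaw in a stated rule. For a two-dose participant whose AE has a missing start day in the dose-2 month, or a missing day and month in a year containing only dose 2, and whose stop date shows that it ended before dose 2, Appendix 2 gives an impossible start date. It puts the event in the post-dose-2 window, with possible reclassification as solicited.

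The size is not given and is probably small. That judgement rests on three things: complete start dates are untouched, most of the relevant onsets fall outside routine collection, and the contradiction is provable only when the stop date is known well enough to precede dose 2. The documents give no frequency of partial AE dates. No effect on the efficacy analyses follows, and no directional bias between H4:IC31 and Placebo is shown. It is a minor refinement, worth making because it costs almost nothing.

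**What to change.** Add to both the day-missing and the day-and-month-missing rows of Appendix 2:

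> If the complete or partial stop date shows that the event ended before the Day 56 vaccination, do not impute the start to the Day 56 vaccination. Impute it to the later of the first day of the known month (or year) and the Day 0 vaccination date, and assign the reporting window from that date.

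In the first example this gives 1 Mar 2015 (Day 35), and in the second 1 Jan 2015 (Day 47). Both precede the stop date and lie outside the dose-2 window. Naming Day 56 keeps the rule defined for BCG participants and for dose-1-month events, where there is no earlier dose to fall back on. First-of-month is already the appendix's choice for events between doses.

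Also state in Section 16.1.8 whether dose at onset uses the imputed date when the collected date is partial.

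Cost: two short SAP additions and a line or so of code, using data already collected.

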### APPENDIX 3. SOLICITED AND INJECTION SITE ADVERSE EVENT (AE)

#### PREFERRED TERMS AND CODES

Relevant Treatment Group	Solicited or Injection Site AE	Solicited AE Category	Preferred Term	Preferred Term Code
Placebo H4:IC31 BCG	Solicited AE	Systemic	Pyrexia	10037660
			Myalgia	10028411
			Arthralgia	10003239
			Fatigue	10016256
			Headache	10019211
			Decreased appetite	10061428
			Urticaria	10046735
			Chills	10008531
BCG	Injection site AE	Local	Lymphadenopathy	10025197
			Vaccination site pain	10068879
			Vaccination site erythema	10059079
			Vaccination site swelling	10069620
			Vaccination site ulcer	10069621
Placebo H4:IC31	Injection site AE	Local	Vaccination site discharge	10069560
			Injection site pain	10022086
			Injection site erythema	10022061
			Injection site swelling	10053425
			Injection site ulcer	10022105
			Injection site discharge	10065600

Document: Aeras\_C-040-404\_SAP\_V2\_0

Author: [name]

Version Number:

2.0

Version Date:

29SEP2017

Template No: CS\_TP\_BS016 – Revision 3

Reference: CS\_WI\_BS005

Effective Date: 01May2012

Copyright © 2012 Quintiles Transnational Corp. All rights reserved.

The contents of this document are confidential and proprietary to Quintiles Transnational Corp. Unauthorized use, disclosure or reproduction is strictly prohibited.

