### 16.1.2. ALL ADVERSE EVENTS (AEs)

The following tables are planned for presentation:

- Overview of AEs:
  - o Number and percentage (%) of participants in each of the following categories (participants with multiple events in each category are counted only once in each category):
    - Any AE.
    - Any solicited AE.
    - Local solicited AE.
    - Systemic solicited AE.
    - SAE.
    - SAE with outcome of death.
    - Related AE.

---

Document: Aeras\_C-040-404\_SAP\_V2\_0

Author: [name]

Version Number:

2.0

Version Date:

29SEP2017

Template No: CS\_TP\_BS016 – Revision 3

Reference: CS\_WI\_BS005

Effective Date: 01May2012

Copyright © 2012 Quintiles Transnational Corp. All rights reserved.

The contents of this document are confidential and proprietary to Quintiles Transnational Corp. Unauthorized use, disclosure or reproduction is strictly prohibited.

- Severe AE.
- Related, severe AE.
- AE leading to premature study discontinuation.
- Adverse events of special interest (AESI).
- Percentage (%) of participants will be calculated relative to the total number of participants in the Safety analysis set per treatment group and cohort.
- 95% CIs:
  - Calculated for single proportion using mid-p binomial option (Clopper-Pearson method with mid-p correction).
- Number of events in each of the aforementioned categories (participants with multiple events in each category are counted multiple times in each category).
- This output will be repeated for the Safety and Immunogenicity Cohort as well as the Correlates Cohort.

All AE incidence tables will be sorted by:

- SOC (descending frequency of total number of participants with events reported).
- PT (descending frequency of total number of participants with events reported within each SOC).

All AE incidence tables presented by PT only will be sorted by:

- PT (descending frequency of total number of participants with events reported).

The following incidence table will be presented by SOC and PT:

- Incidence of AEs:
  - Number and percentage (%) of all participants with AEs summarized by SOC and PT.
  - Includes all AEs within the post-vaccination reporting windows (refer to Section 16.1.9: Adverse Event (AE) Post-vaccination Reporting Window for details on the derivation of post-vaccination reporting window).
  - This table will be repeated for the Safety and Immunogenicity Cohort.

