#### 16.1.2.1. Severity

Severity will be reported on the Adverse Events eCRF as mild, moderate or severe (increasing severity).

Missing severities will not be regarded as 'worst case' severity. If any missing severity is present in the data transfer, the severity will remain missing and will be counted under the missing category in the by-severity tables. Participants with multiple events in each SOC/solicited AE category and PT are counted only once in each SOC/solicited AE category and PT at highest severity.

---

Document: Aeras\_C-040-404\_SAP\_V2\_0

Author: [name]

Version Number:

2.0

Version Date:

29SEP2017

Template No: CS\_TP\_BS016 – Revision 3

Reference: CS\_WI\_BS005

Effective Date: 01May2012

Copyright © 2012 Quintiles Transnational Corp. All rights reserved.

The contents of this document are confidential and proprietary to Quintiles Transnational Corp. Unauthorized use, disclosure or reproduction is strictly prohibited.

For the overview of unsolicited AEs by severity, time of onset and relationship table, AEs with missing severity will be considered. The participant will be counted in the missing category if the all severities are reported as missing for the relevant participant.

The following incidence tables are planned for presentation by SOC and PT:

- Incidence of AEs by highest severity.
- Incidence of AEs by highest severity by dose (refer to 16.1.8: Adverse Event (AE) Dose at Onset (Most Recent Vaccination)).

The following listing will be presented:

- Adverse events of toxicity grade 3/4:
  - o An AE of toxicity grade 3/4 is any AE for which the severity is indicated as severe.

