#### **16.1.9. ADVERSE EVENT (AE) POST-VACCINATION REPORTING WINDOW**

All SAEs and AESIs will be collected through database lock.

All unsolicited AEs will be collected during the 28-day reporting window following each study vaccination. The reporting window is defined in terms of the relevant scheduled study visit coinciding with the 28-day window following the relevant dose.

Solicited systemic adverse events will be collected during the 7-day reporting window following each study vaccination (diary cards will be used for 7 days following each study vaccination for the Safety and Immunogenicity Cohort only).

Solicited and unsolicited local injection site reaction adverse events will be collected:

- BCG treatment group:
  - o 84-day reporting window following study vaccination.
- H4:IC31 and Placebo treatment groups:
  - o 28-day reporting window following each vaccination.

---

Document: Aeras\_C-040-404\_SAP\_V2\_0  
Author: [name]

Version Number: 2.0  
Version Date: 29SEP2017

Template No: CS\_TP\_BS016 – Revision 3  
Effective Date: 01May2012

Reference: CS\_WI\_BS005

Refer to Table 4: General Adverse Event (AE) Post-vaccination Reporting Windows below for the relevant post-vaccination reporting windows as defined in terms of scheduled study visits:

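### For five site reactions, BCG and placebo are tabulated under different preferred terms with no rule combining them, so no row for an individual reaction of these five sets the two arms side by side

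*SAP*

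**What the plan says.** SAP Appendix 3 gives the preferred terms that count as solicited or injection-site events, with a column for the relevant treatment group. Pain, erythema, swelling, ulcer and discharge each appear twice: once with the Vaccination-site prefix ("Vaccination site pain") for BCG, and once with the Injection-site prefix ("Injection site pain") for placebo and H4:IC31. In the available text the treatment-group labels sit about one row out of place, but the pairing of the terms is plain.

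SAP 16.1.4 sets aside the database's own solicited flag: "All AEs will be assigned as either solicited or unsolicited based on the PT", together with the reporting window. Within the local and systemic categories, rows are ordered by "PT (descending frequency of total number of participants with events reported within each solicited AE category". The tables give "Number and percentage (%) of participants with AEs summarized by solicited AE category and PT". Under SAP 16.1.2.1, participants with several events "are counted only once in each SOC/solicited AE category and PT at highest severity". The overview table in SAP 16.1.2 has a row named "Local solicited AE". SAP 16.1.9 gives BCG an "84-day reporting window following study vaccination"; the other two arms have 28 days after each dose.

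The protocol (3.6.3.3 and 5.7) solicits one list of site reactions and does not divide it by arm.

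**The concern.** Safety of both vaccines is a primary objective, and Protocol 7.5.1 describes it by treatment group from counts and percentages of events. With no formal safety comparison, the tables are the result. Local reactions are the most expected effect of BCG revaccination, and the placebo column is where a reader looks for the background rate.

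With the terms split by arm, the placebo cell beside BCG pain or BCG ulcer holds a zero that comes from the coding list. A reader can take it for an observed background of 0%. The Total column and the frequency ordering are also computed on one part of each reaction at a time.

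The pooled local rows do not fully make up for this. Protocol 1.4 reports redness in every subject after BCG in an earlier study, and Protocol 1.6 describes redness, induration and a small ulcer as the normal course. A row for any local reaction may therefore sit near its ceiling in the BCG arm. It could not then separate ulceration or drainage, which the toxicity table grades as 3, from redness.

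**Working it through.** The plan states no figure on this point, so there is none to reproduce. The check sets the terms in Appendix 3 against the rows planned in SAP 16.1.2, 16.1.4 and 16.2.

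**Rows by arm, if coding follows Appendix 3**

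| Terms | Rows | BCG | Placebo | H4:IC31 | Cells zero by coding |
|---|---|---|---|---|---|
| Vaccination site | 5 | observed | zero | zero | 5 × 2 = 10 |
| Injection site | 5 | zero | observed | observed | 5 × 1 = 5 |
| All | 10 | | | | 15 of 10 × 3 = 30 |

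Rows in which both BCG and placebo can be non-zero: 0 of 10.

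**Total column.** SAP Section 8 includes a Total group in table presentations. Take the planned 330 per arm (Protocol Table 2-1, SAP Table 1) and a denominator of 990:

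- a Vaccination-site row cannot exceed 330/990 = 33.3%;
- an Injection-site row cannot exceed (330 + 330)/990 = 66.7%.

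For any true rates, the Vaccination-site Total is the BCG rate divided by 3, and the Injection-site Total is the sum of the placebo and H4:IC31 rates divided by 3. As an illustration only, with rates that are assumed and not in the documents, let pain be 60% in BCG, 20% in placebo and 40% in H4:IC31. The arm cells, in the order BCG, placebo, H4:IC31, print as 60/0/0 in one row and 0/20/40 in another. The Totals are 60/3 = 20.0% and (20 + 40)/3 = 20.0%. Combined, pain has a Total of (60 + 20 + 40)/3 = 40.0%. A sort on total frequency would rank it as two events at 20.0% instead of one at 40.0%.

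**Rows that do set BCG beside placebo**

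- The local solicited row of the overview table (SAP 16.1.2), with a 95% interval.
- The local category row of the solicited tables (SAP 16.1.4), each participant counted once.
- Possibly lymphadenopathy, which has a single term. The displaced labels leave open whether Appendix 3 assigns it to BCG alone or to all arms; the protocol solicits it without naming an arm.

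The site assessments recorded under common names in every arm (SAP 16.2) are planned only as a listing.

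**After pairing the terms.** Ten rows become five, each open to all three arms. Cells that are zero by coding fall from 15 of 30 to 0 of 5 × 3 = 15. The unequal collection windows remain.

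**The case against.** The strongest reply is that this is a matter of layout and that no information is lost. Each arm's percentage for each reaction is printed in the same table, in rows whose names differ by one word, so the placebo background rate can be found. The analysis is descriptive, and no test or decision rule needs a shared row. This stands, and it limits the point to an improvement in presentation.

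It can also be said that separate rows are right because the exposures differ: one open-label intradermal BCG dose with 84 days of local follow-up, against two blinded intramuscular doses with 28 days after each. The difference is real, but it argues for a footnote. The plan already pools the two term sets over the same unequal windows in its category and overview rows.

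The table shells, which SAP Section 8 says define format and content, might already group the terms. They were not available. The SAP text contains no such rule.

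A reader might go further and infer that no row of the local tables compares BCG with placebo, or that every row carries artificial zeros. The documents do not support that: the overview and category rows pool both term sets, and lymphadenopathy is not split.

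A reader might also infer that a BCG reaction coded with an Injection-site term would be lost from the solicited tables. That needs coding to cross arms and the treatment-group column to work as a filter. SAP 16.1.4 sets solicited status by term and window and does not mention arm.

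**Conclusion.** The point holds for the preferred-term rows of five reactions: pain, erythema, swelling, ulcer and discharge. None of the 10 rows sets BCG beside placebo, 15 of 30 arm cells are zero by coding, and the Total column and sort order are split. The arms are compared only in pooled local rows that do not identify the reaction, and possibly in the lymphadenopathy row.

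This assumes that coding follows Appendix 3, that no participant with a mixed regimen (SAP 5.2) puts a term in another arm's column, and that the table shells do not already merge the pairs. The Total-column limits also assume the planned 330 per arm.

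The placebo rate is reported, in a different row, so the plan does not suppress it. No test, power figure or efficacy result is affected. It is a cheap improvement to the descriptive tables that serve a primary safety objective.

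**What to change.** In SAP Appendix 3 and 16.1.4:

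- Map each Vaccination-site and Injection-site pair to one analysis term used in all arms, for example Injection/vaccination site pain.
- State that an event is solicited if either term of the pair is coded, in any arm, subject to the reporting window. This also settles how the treatment-group column is to be read.
- Build the local solicited incidence, severity and relatedness tables on the analysis terms, counting each participant once per analysis term.
- Keep the MedDRA preferred terms in the listings.
- Footnote the collection windows: BCG, 84 days after one dose; placebo and H4:IC31, 28 days after each of two doses.

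The cost is one mapping column in the programming specification and matching row labels in the shells. There are two small downsides. Five rows no longer carry a literal MedDRA term, and the percentages now side by side cover unequal windows, which is why the footnote is needed.
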